Molecular Subtyping of Extensive Stage Small Cell Lung
Cancer and Relevant Clinical Significance
(The MOSAIC study)

2022.3.29

Version 1.0

Objective:

- (1) Validating the predictive value of transcriptome-based molecular subtyping of extensive stage small cell lung cancer(SCLC) for the efficacy of PD-1/PD-L1 inhibitor in the first line setting.
- (2) Exploring the differences of immune microenvironment between different SCLC subtypes to reveal the mechanisms of immunotherapy resistance of SCLC

Protocol:**1.1 Design**

This study is a retrospective observational study without intervention in clinical treatment. In prior study, the transcriptomic data was used to classify SCLC into four subtypes, which might have different sensitivity to immunotherapy. Therefore, molecular subtyping could be used as an important biomarker for predicting efficacy of immunotherapy, which need further validation. This study will explore the predictive value of different subtypes of SCLC for immunotherapy and mechanisms of immunotherapy resistance of SCLC. Extensive stage SCLC patients receiving first-line standard treatment will be enrolled in this study. Baseline tumor tissue samples and peripheral blood samples will collected for transcriptome and immunohistochemistry analysis etc. Based on these results, patient will be classified into four subtypes and efficacy and safety of treatment will be recorded. We will compare the efficacy between different subtypes of SCLC and analyze whether molecular typing could predict the efficacy of immunotherapy; Compare the differences in immune microenvironment of different subtypes of SCLC to reveal the mechanism of immunotherapy resistance. The treatment regimen involved in this study follows guidelines for the first-line treatment of extensive stage SCLC: cisplatin+etoposide or carboplatin+etoposide with or without approved PD-(L)1 inhibitor for SCLC. Treatment options are determined by the patient's supervising physician.

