1.2 Patients**Inclusion Criteria:**

- 1) Male or female, aged 18 to 100 years
- 2) Patients with untreated advanced small cell lung cancer clearly diagnosed by histopathology
- 3) Be able to provide tumor biopsy tissue sample for molecular analysis
- 4) ECOG score: 0 ~2;
- 5) Expected survival of more than 3 months.
- 6) Has at least 1 measurable or evaluable tumor lesion with a longest diameter ≥ 10 mm at baseline (in case of lymph nodes, a shortest diameter ≥ 15 mm is required) according to RECIST v1.1
- 7) Received first-line chemotherapy or chemotherapy + PD-(L)1 inhibitor and be able to provide complete treatment information and efficacy evaluation results.
- 8) Voluntary signed informed consent and expected good compliance.

Exclusion Criteria:

- 1) Patient unable to tolerate chemotherapy.
- 2) Patients unable to provide tumor tissue samples for testing
- 3) Patients with other malignant tumors or a history of other malignant tumors
- 4) Patients have any other reason to be unfit to participate in this study.

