1.3 Endpoint and follow up

Primary endpoint: Progression-free survival

Secondary endpoint: Overall survival; Objective response rate; molecular subtyping and tumor microenvironment biomarkers.

Follow-up plan:

- 1) Patients will be reviewed every 2 cycles during treatment to assess effectiveness and record vital signs and test results.
- 2) Patients will be reviewed periodically every 3 months after completion of treatment until disease progression.
- 3) After disease progression, patients will continue to be followed up every 3 months to record post treatment until die or lost follow-up.

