1.4 Sample Size

Chemotherapy: 80-100 cases.

Immunotherapy+chemotherapy: 80-100 cases.

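### Inclusion 7, read literally, ties entry to results that exist only after treatment starts; where early deaths are left out, absolute PFS, OS and ORR read too favourably

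*Combined protocol and SAP*

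**What the plan says.** Section 1.2, inclusion 7, admits patients who have had first-line treatment and who "be able to provide complete treatment information and efficacy evaluation results". Section 1.1 states: "This study is a retrospective observational study without intervention in clinical treatment". Section 1.3 sets the assessment schedule: "Patients will be reviewed every 2 cycles during treatment to assess effectiveness". PFS is the primary endpoint, and OS and ORR are among the secondary ones.

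Other wording looks forward. Inclusion 2 asks for patients not yet treated. Inclusion 5 asks for "Expected survival of more than 3 months". Inclusion 8 asks for consent and anticipated good compliance. Section 1.6 puts the signing of consent in the future tense. Section 1.3 plans future visits: "After disease progression, patients will continue to be followed up every 3 months".

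Section 1.5 does not say how a death before the first assessment counts for PFS, who is in the ORR denominator, or what happens to patients with no assessment. No section says that a recorded death satisfies inclusion 7, and none gives the timing of consent relative to the start of treatment.

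**The concern.** Eligibility should rest on what is known when follow-up starts. Inclusion 7 instead refers to results produced during follow-up. A patient who dies before the first review is a PFS event, an OS event and a non-responder. If such patients fail inclusion 7, the cohort loses its worst outcomes and all three endpoints shift in the favourable direction.

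The effect is limited to that group. Patients who progress at the first review have a result and stay in. Patients who leave for reasons unrelated to prognosis barely affect PFS or OS. For ORR they matter only through the denominator: with 5% such leavers, a rate of 60% among evaluable patients becomes 0.60 × 0.95 = 57% if leavers count as non-responders.

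**Working it through.** **Plan's own figures.** The only planning figure is the group size (section 1.4: "Immunotherapy+chemotherapy: 80-100 cases", and the same range for chemotherapy alone). It has no effect size, power or event count behind it, so there is nothing to reproduce. Every survival input below is an assumption.

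**Share lost, d.** With exponential OS of median m and first review at R, d = 1 − 2^(−R/m). Cycle length is not stated; R = 1.38 and 1.84 months correspond to two cycles of 21 and 28 days.
- m = 15, R = 1.38: d = 0.062.
- m = 8, R = 1.84: d = 0.147.

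These values ignore the eligibility filters, so the range is extended down to 0.02. The range used is 0.02–0.15.

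**Median OS.** After R, the curve among those kept is S(t)/(1 − d). Setting it to 0.5 gives a median of m × [1 − log2(1 − d)].
- d = 0.02: factor 1.029.
- d = 0.05: 1.074.
- d = 0.10: 1.152.
- d = 0.15: 1.234.

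**ORR.** The excluded patients are non-responders, so the observed rate is ORR/(1 − d). For 60%: 0.60/0.98 = 61.2%; 0.60/0.85 = 70.6%.

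**Patients never counted.** N × d/(1 − d).
- N = 80: 1.6 to 14.1.
- N = 100: 2.0 to 17.6.

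**Median PFS.** When progression is found only at reviews, the median moves in steps and the OS factor does not apply. Simulation, with latent progression median 6 months, death median 12 months and all deaths before R dropped:
- R = 1.38, 7.7% lost: 4.14 becomes about 5.1 months (factor about 1.24; the OS formula would give 1.12).
- R = 1.84, group with HR 0.6, 6.2% lost: 7.36 stays 7.36 (factor 1.00).

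**Hazard ratios, proportional hazards.** Same model, 400,000 per group, Cox regression, censoring at 24 months, same rule in both groups. Full cohort against selected cohort:

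| True HR | R | PFS | OS |
|---|---|---|---|
| 0.6 | 1.38 | 0.614 / 0.615 | 0.601 / 0.602 |
| 0.6 | 1.84 | 0.616 / 0.618 | 0.597 / 0.597 |
| 1.0 | 1.38 | 0.999 / 0.999 | 1.003 / 1.003 |
| 1.0 | 1.84 | 0.999 / 0.998 | 1.001 / 1.000 |

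The largest shift is 0.002. With HR 0.6 and R = 1.38, early death differs between groups (7.6% against 4.6%), yet the HR is stable.

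**Hazard ratios, non-proportional hazards.** Death hazards equal until R and HR 0.6 afterwards, median 10 months. Early death is then equal in the two groups (about 9% at R = 1.38). Dropping those deaths moves the HR from 0.638 to 0.598 (R = 1.38) or from 0.653 to 0.600 (R = 1.84). Proportionality and the way the rule is applied decide the matter, not simply whether early death is equal.

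**The case against.** The strongest reply is that inclusion 7 only asks for patients whose data can be supplied. Inclusion 3 uses the same phrasing for tissue, and the forward-looking wording elsewhere fits enrolment before treatment. On that reading the bias is small, unless the criterion is applied later to remove patients with no assessment. This stands as a reason for moderate confidence. It does not settle the matter, because the past tense of inclusion 7 and the retrospective label point the other way.

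Second, early death should be uncommon. Inclusion 5 and ECOG 0–2 apply to everyone, and exclusion 1 removes a "Patient unable to tolerate chemotherapy". This makes the 15% end unlikely. But expected survival is a forecast and does not rule out actual early death.

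Third, objective 1 is about prediction and compares subtypes, and no absolute target is set for PFS, OS or ORR. This also stands. A reader might infer that the subtype comparison itself is biased, especially since "Treatment options are determined by the patient's supervising physician". The documents do not support that: they give no early-death or exclusion counts by subtype or regimen, and under proportional hazards with one rule for all, the hazard ratio hardly moves. Nor do they guarantee that the comparison is safe, since neither proportional hazards nor uniform application of the rule can be judged from them.

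**Conclusion.** The point holds as a conditional one. Read literally, inclusion 7 allows early deaths to be dropped and nothing in the plan offsets this. The direction is clear wherever it happens: absolute OS and ORR read too favourably, and PFS moves the same way, though its median may not shift when read at scheduled reviews.

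The size is illustrative. It rests on an assumed early-death share, exponential OS, and exclusion of every early death; if some are kept, the shift is smaller. The OS factor of 1.03–1.23 should not be carried over to PFS.

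A reader might also infer that patients were enrolled only after surviving to a late consent. The documents do not say so. If consent did follow treatment start, only patients alive at consent could enter. That would be a separate selection affecting both OS and PFS, and it is a reason to state the timing.

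This should be corrected, but it does not undermine the main comparison on the evidence available.

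**What to change.** **Eligibility (1.2).** Reword inclusion 7 to require at least one dose of first-line chemotherapy, with or without a PD-(L)1 inhibitor, and delete the conditions on complete information and efficacy results. Enrol consecutive eligible treated patients with baseline tissue within each regimen until its 80–100 is reached. A fixed date window could miss either target, because physicians choose the regimen.

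**Analysis (1.5).** Count death before the first assessment as a PFS event. Count unevaluable patients as non-responders for ORR. Report the number without an assessment by subtype and regimen.

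**Design and consent (1.1–1.3, 1.6).** Reconcile the retrospective label and the past tense of inclusion 7 with the requirement for untreated patients and the follow-up plan, and state when consent is taken. Only if consent follows treatment start, choose one of two routes:
- delayed entry at consent for OS, and for PFS among patients progression-free at consent; or
- an ethics waiver that allows deceased patients to be included.

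**Cost.** An ethics amendment, some less complete records, and less favourable absolute PFS, OS and ORR. If delayed entry is needed, patients who progressed before consent are lost to the PFS analysis, and the software named in 1.5 must be checked for its handling of entry times.

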1.3 Endpoint and follow up

Primary endpoint: Progression-free survival

Secondary endpoint: Overall survival; Objective response rate; molecular subtyping and tumor microenvironment biomarkers.

Follow-up plan:

- 1) Patients will be reviewed every 2 cycles during treatment to assess effectiveness and record vital signs and test results.
- 2) Patients will be reviewed periodically every 3 months after completion of treatment until disease progression.
- 3) After disease progression, patients will continue to be followed up every 3 months to record post treatment until die or lost follow-up.

1.4 Sample Size

Chemotherapy: 80-100 cases.

Immunotherapy+chemotherapy: 80-100 cases.

1.5 Statistics

All measurements will be expressed as mean \pm standard deviation. COX regression analysis was used to examine the correlation between immune indicators and efficacy, and one-way ANOVA will be used to analyze the correlation between the variables and the efficacy of immunotherapy or adverse effects. The number of different cell types will be compared between patient subgroups using the Wilcoxon rank-sum and Jonckheere-Terpstra tests. Differences between the two groups will be analyzed using a two-sided t-test. Categorical variables and continuous variables will be calculated according to frequency counts and median values respectively. The statistical analysis software is GraphPad Prism and SPSS 19.0. $P < 0.05$ will be considered statistically different.

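### Objective 1 is a predictive claim about subtype, but section 1.5 assigns no method that tests whether subtype modifies the treatment effect on PFS or OS

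*Combined protocol and SAP*

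**What the plan says.** The first objective is "Validating the predictive value of transcriptome-based molecular subtyping of extensive stage small cell lung cancer(SCLC) for the efficacy of PD-1/PD-L1 inhibitor" in the first-line setting. Section 1.1 puts it into practice as follows: "We will compare the efficacy between different subtypes of SCLC and analyze whether molecular typing could predict the efficacy of immunotherapy". Patients receive platinum-etoposide with or without an approved inhibitor, and "Treatment options are determined by the patient's supervising physician". Section 1.1 sets four subtypes; section 1.4 plans 80-100 patients on chemotherapy and 80-100 on chemotherapy plus immunotherapy.

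Section 1.3 states "Primary endpoint: Progression-free survival", with OS and ORR among the secondary endpoints. For PFS, "Patients will be reviewed periodically every 3 months after completion of treatment until disease progression". After progression, follow-up continues "to record post treatment until die or lost follow-up".

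Section 1.5 is the whole statistics section. It assigns methods as follows:

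- Cox regression: immune indicators (not defined) against efficacy.
- One-way ANOVA: "one-way ANOVA will be used to analyze the correlation between the variables and the efficacy of immunotherapy or adverse effects".
- Wilcoxon rank-sum and Jonckheere-Terpstra: cell-type numbers between patient subgroups.
- Two-sided t-test: differences between two groups, with neither the groups nor the outcome named.
- Means with SD, frequency counts and medians: description only.

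No section mentions a subtype-by-treatment term, Kaplan-Meier estimates, a log-rank test, a censoring rule or covariate adjustment.

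**The concern.** A predictive marker changes the treatment effect; a prognostic marker changes the outcome whatever the treatment. Only a comparison of the treatment effect across subtypes tells them apart, and that needs both treatment groups in one analysis. The study collects both groups, but section 1.5 never says how they will be combined.

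The method that the section does attach to immunotherapy efficacy is unsuited to the primary endpoint. ANOVA treats a censored time as an observed one, and the one-way form has a single factor. What is at stake is the main conclusion: a subtype that does well on chemotherapy and on chemo-immunotherapy alike could be published as a selection marker for the inhibitor.

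**Working it through.** **1. Do the named methods cover the objective on any reading?**

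- *Literal.* ANOVA is applied to PFS and OS, which can be censored, and to ORR and adverse-event incidence, which are binary. There is no interaction.
- *Generous.* ANOVA compares a continuous marker across response or toxicity categories, which suits it. PFS and OS by subtype and treatment then have no named method.
- *Most generous.* Subtype counts as an immune indicator and efficacy includes PFS and OS. Cox then covers subtype against PFS, but treatment is not in the model as described.

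On all three, the test of effect modification is missing.

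**2. Why a subtype test within the immunotherapy group does not fill the gap.** Let b be the subtype HR on chemotherapy and r the ratio of treatment HRs (that subtype against the others). The subtype HR within the immunotherapy group is b × r.

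- Prognostic only: b = 0.5, r = 1, so b × r = 0.5.
- Predictive only: b = 1, r = 0.5, so b × r = 0.5.

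The within-group test sees the same HR in both cases. Only a test of r separates them.

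**3. Size of the problem (simulation on assumed inputs).** The documents give no PFS median, follow-up time or subtype shares. Assumed: exponential PFS, median 4, 5 or 7 months, uniform censoring over 3-24 months, and 80 or 100 per treatment group (section 1.4). With equal shares there are 80/4 = 20 to 100/4 = 25 patients per subtype per group. An unequal split of 56/20/14/10% is an assumed alternative. There were 1500 runs per scenario, with Monte Carlo error of at most about 2.5 points. One subtype has HR 0.5 in both treatment groups, so r = 1 and any finding of predictive value is false.

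| Subtype split | Subtype test within immunotherapy, significant | 3-df Cox interaction test, significant |
|---|---|---|
| Equal | 37-56% | 5-7% |
| Unequal, effect in largest subtype | 46-70% | 6-8% |
| Unequal, effect in smallest subtype | 22-30% | 6-8% |

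A separate 1000-run simulation of the equal split gave 38-56% against 6-7%.

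**4. Power of the interaction test if it is added** (HR 0.5 in one subtype, immunotherapy group only, same assumptions): 24-33% with equal shares (19-31% in the separate simulation), 31-43% for the largest subtype and 14-19% for the smallest. With follow-up of 12-36 months and median 5 the figures are 31-37%, 38-48% and 15-20%.

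A hand check for one pre-named subtype against the rest, a 1-df test: SE of ln r = sqrt(4 / (D × p × (1 − p))), with D events and subtype share p. Assume 70-90% of patients have an event, so D = 160 × 0.7 = 112 to 200 × 0.9 = 180, and p = 0.25.

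- D = 112: SE = sqrt(4/21) = 0.436; power = Φ(0.693/0.436 − 1.96) = 36%.
- D = 180: SE = sqrt(4/33.75) = 0.344; power = Φ(0.693/0.344 − 1.96) = 52%.
- Events for 80% power: (1.96 + 0.84)² × 4 / (0.1875 × 0.693²) ≈ 349.

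**5. Can the data carry the model?** Parameters: 3 subtype + 1 treatment + 3 interaction + 3 covariates = 10. For hazard λ = ln 2 / median, the censored share is (e^(−3λ) − e^(−24λ)) / (21λ).

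- Median 7, HR 1: λ = 0.0990, share 0.31.
- Median 7, HR 0.5: λ = 0.0495, share 0.54.
- HR 0.5 in one of four equal subtypes, both groups: 0.75 × 0.31 + 0.25 × 0.54 ≈ 37% censored. With 160 patients, 160 × 0.63 ≈ 101 events, about 10 per parameter.
- HR 0.5 in the 56% subtype, both groups: 0.44 × 0.31 + 0.56 × 0.54 ≈ 44% censored. 160 × 0.56 ≈ 90 events, about 9 per parameter.
- ECOG 0-2 entered as three categories makes 11 parameters: 90/11 ≈ 8.2.

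**The case against.** The strongest reply is that this is a short observational protocol, that it does name a method for censored data, and that the ANOVA sentence may only mean continuous markers compared across response or toxicity groups. That reading is possible, and on it ANOVA is appropriate. Even on the literal reading, simulated type I error of ANOVA on observed PFS within one treatment group was 4-6% when follow-up was equal. With follow-up of 12-36 months, equal subtype shares and median 5, almost no power was lost (53-63% against 53-64% for log-rank). So the ANOVA wording alone is not the main harm. None of this supplies a test of effect modification.

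Three stronger readings are tempting, and the documents do not support them:

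- *That the plan will compare PFS by t-test, with inflated false positives.* The t-test sentence names no outcome and no groups. The inflation also needs follow-up to differ between the groups, which the documents neither state nor exclude.
- *That a treatment comparison of PFS is a planned aim left without a method.* Neither objective asks whether adding the inhibitor improves outcome. Treatment enters Objective 1 only through its interaction with subtype.
- *That adding the interaction test would settle Objective 1.* On the assumptions above its power is low, and its false-positive rate can be slightly above nominal (up to 8%).

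The reply is also right that every magnitude here depends on assumed medians, follow-up and shares. The gap itself rests on the text alone.

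**Conclusion.** The point holds and should be corrected before the analysis. Section 1.5 contains no test of whether subtype modifies the treatment effect on PFS or OS, so the plan as written cannot separate a prognostic subtype from a predictive one. That conclusion needs no numerical assumption.

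Its size does. With an equal split, a purely prognostic HR of 0.5 would look like a finding within the immunotherapy group in about 37-56% of runs, against about 5-7% with the interaction test. The sample size in section 1.4 comes with no power, effect size or event count, so there is no planned figure to reproduce. A reader might infer that the plan commits to an invalid test of PFS. The text is too loose to show that; what it shows is that the required test is absent.

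**What to change.** Replace the efficacy part of section 1.5 with the following.

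- **PFS and OS:** Kaplan-Meier estimates by subtype and treatment, and a Cox model with subtype, treatment and their interaction. Adjust for age, sex and ECOG score, because treatment is the physician's choice. All three appear in the eligibility criteria of section 1.2 (for instance "Male or female, aged 18 to 100 years").
- **Test of predictive value:** the 3-df likelihood-ratio interaction test, reported with subtype-specific treatment HRs and 95% CIs.
- **Censoring:** patients without an event are censored at the last progression-free assessment for PFS and at last contact for OS.
- **ORR and adverse-event incidence:** Fisher exact test or logistic regression.
- **t-test and ANOVA:** kept for uncensored continuous measures.
- **Limits to state in advance:** power of the interaction test is roughly 14-43% for an HR of 0.5 in one subtype under the 3-24 month assumptions, so a null result does not exclude predictive value. Unmeasured confounding remains after adjustment. Events per parameter may be only about 9-10, so enter ECOG with few parameters and report sparse subtypes descriptively; a 10% subtype would have 8-10 patients per treatment group.

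The cost is SAP wording and a little analysis work. No new patients or data items are needed, and clinical management does not change.

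### Minor: section 1.5 relates adverse effects to other variables by one-way ANOVA with no common observation window or exposure adjustment, so longer time on treatment can pass for a link with adverse effects

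*Combined protocol and SAP*

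**What the plan says.** Section 1.1 (Design) says that "patient will be classified into four subtypes and efficacy and safety of treatment will be recorded". It also says that the subtypes may differ in sensitivity to immunotherapy and that the treating physician chooses the regimen.

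Section 1.3 makes PFS the primary endpoint. Reviews take place every 2 cycles during treatment, then every 3 months until progression.

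Section 1.5 deals with adverse effects in one clause: "one-way ANOVA will be used to analyze the correlation between the variables and the efficacy of immunotherapy or adverse effects". Cox regression is named only for efficacy: "COX regression analysis was used to examine the correlation between immune indicators and efficacy". The threshold is P<0.05.

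No section defines the adverse-effect measure, a grading scale, a collection window, an event rate per unit of time, a time-to-first-event method, or the handling of progression and death before an event.

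**The concern.** Adverse effects accumulate with time on treatment. Comparing the share of patients with an event, or the number of events, is fair only if the groups were observed on treatment for similar lengths of time. The study looks for a factor, molecular subtype, that separates patients by time to progression. If that factor exists and treatment continues until progression, patients in the better-responding subtype are exposed for longer. They are also seen more often, because the 2-cycle reviews last as long as treatment does.

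The result could be a reported association between subtype (or an immune marker that tracks it) and adverse effects that reflects only exposure. For the same reason, adverse effects could appear to go with better efficacy.

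**Working it through.** The plan gives no figure to reproduce: there is no adverse-effect rate, treatment duration or power calculation. The check is therefore an illustration.

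**Inputs from the documents.** Section 1.4: "Chemotherapy: 80-100 cases" and "Immunotherapy+chemotherapy: 80-100 cases". Section 1.1: four subtypes. Section 1.5: threshold 0.05.

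**Assumptions.** Subtypes of equal size within one treatment group, so 80/4 = 20 to 100/4 = 25 each. The same constant risk h of a first event per month in every subtype, with h from 0.03 to 0.10. Exponential time on treatment, ending at progression. Median PFS of 4 months in three subtypes and 8 in one.

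**Step 1: share with an event.** P = h/(h + λ), with λ = ln 2/median. This gives λ = 0.693/4 = 0.1733 and λ = 0.693/8 = 0.0866.

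| h per month | median 4 months | median 8 months |
|---|---|---|
| 0.03 | 0.03/0.2033 = 14.8% | 0.03/0.1166 = 25.7% |
| 0.06 | 0.06/0.2333 = 25.7% | 0.06/0.1466 = 40.9% |
| 0.10 | 0.10/0.2733 = 36.6% | 0.10/0.1866 = 53.6% |

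The monthly risk is identical within each row.

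**Step 2: how often the planned test rejects.** Simulated one-way ANOVA on event yes/no across the four subtypes gives P<0.05 in about 14-21% of studies. A second setting, with mean time on treatment of 5, 5, 5 and 10 months, gives 14-16% at 0.05 per month and 16-19% at 0.10. With equal time on treatment ANOVA rejects in about 4-6%. In the second setting and its equal-time counterpart, comparing events per person-month rejects in about 4-7%. The excess therefore comes from exposure and not from the F test.

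**Step 3: treatment stops at 4 months in all groups.** P = [h/(h + λ)] × [1 − exp(−4(h + λ))]. At h = 0.06 this is 0.257 × (1 − exp(−0.933)) = 15.6%, against 0.409 × (1 − exp(−0.587)) = 18.2%. Comparing the long-PFS subtype with the other three pooled (20 v 60 to 25 v 75), rejection is about 6-8%. Without the stop, the same pooled comparison rejects in about 21-33%.

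**Step 4: early toxicity only.** If all risk falls in the first 3 months and every group stays on treatment that long, the shares are equal. At 0.05 per month, 1 − exp(−0.05 × 3) = 13.9% in both, and the bias is gone.

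**Step 5: direction of the ANOVA.** The sentence does not say whether adverse effects are the outcome or the grouping factor. For two yes/no variables this makes no difference: F = (n − 2)r²/(1 − r²) depends only on their correlation r. For a continuous immune marker grouped by adverse-effect status, the same artefact arises if the marker goes with longer treatment. Its size was not calculated.

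**The case against.** The strongest objection concerns what the sentence commits the study to. It can be read as ordinary ANOVA, with a continuous immune variable as outcome and adverse-effect category as the grouping factor. Section 1.1 promises to compare efficacy between subtypes, whereas safety is only recorded. This stands against the reading a reader might infer, that the plan will rank subtypes or regimens by toxicity and call the longest-treated group the most toxic. The documents do not specify that comparison. It does not remove the exposure problem, which can arise in either direction (Step 5).

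A reader might also infer a very large error between the two regimens. With 90 v 90, one regimen stopping at 4 months and the other continuing to progression (median 6), false positives would be about 60-80%. The plan does not explicitly call for that comparison. Its general sentence, "Differences between the two groups will be analyzed using a two-sided t-test", does not mention adverse effects, and the durations are assumed. The figure should not be attached to this plan.

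Treatment to progression is itself an assumption. Section 1.3 provides for reviews after treatment is completed and before progression, so some patients finish earlier. This stands: Step 3 shows how far the excess shrinks. Toxicity that itself stops treatment could mask or reverse the effect.

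Finally, ANOVA is not the source of the bias. It holds about 5% when exposure is equal, and Fisher's exact test on the same open-ended yes/no outcome would be biased in the same way. This also stands, and it is why the window matters more than the choice of test.

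**Conclusion.** The point holds as a minor one. Section 1.5 gives adverse effects no common window and no exposure adjustment, in a study whose premise makes unequal time on treatment plausible. Under equal constant monthly risk, treatment to progression and a doubling of median PFS in one of four subtypes, the false-positive rate is about 14-21% rather than 5%. It is close to nominal under a short common course, and nominal if toxicity is early only. The true size cannot be fixed from the documents.

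Adverse effects are not a listed primary or secondary endpoint, and neither objective mentions safety. The conclusions on PFS, OS and ORR do not depend on this clause.

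**What to change.** In section 1.5, define the adverse-effect outcome as any event, or any event of a stated grade, within a fixed window from first dose that is common to all patients. Analyse it by Fisher's exact test or logistic regression in place of ANOVA, and state which variable is the outcome.

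Where event and dosing dates are available, add as support either time to first event censored at end of exposure, or exposure-adjusted event rates. If adverse effects are related to PFS or OS, treat them as time-dependent or use a landmark analysis.

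The cost is a change of wording plus abstraction of event dates and first and last dose dates from the records. Section 1.2 already requires complete treatment information, but whether onset dates can be recovered retrospectively is not stated. The small downside is that events after the window move to the supporting analysis.
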